### 3.3.5. Health Quality of Life

The FACT-BMT version 4.0 instrument is comprised of a general core questionnaire, the FACT-G, which evaluates the health-related quality of life (HQL) of patients receiving treatment for cancer, and a specific module, BMT Concerns, which addresses disease and treatment-related questions specific to bone marrow transplant. The FACT-G consists of four subscales developed and normed in cancer patients: Physical Well-being, Social/Family Well-being, Emotional Well-being, and Functional Well-being. Each subscale is positively scored, with higher scores indicating better functioning. The FACT-BMT Total, which is the grand total of all items in the FACT-G and BMT modules, will be used as the outcome measure in summarizing the FACT-BMT data.

The MOS SF-36 instrument is a general assessment of health quality of life with eight components: Physical Functioning, Role Physical, Pain Index, General Health Perceptions, Vitality, Social Functioning, Role Emotional, and Mental Health Index. Each domain is positively scored, indicating that higher scores are associated with positive outcome. This scale has been widely applied in a variety of outcome studies and is being used in this protocol as a generic measure of quality of life. To facilitate comparison of the results with published norms, the Physical Component Summary (PCS) and Mental Component Summary (MCS) will be used as the outcome measures in summarizing the SF-36 data.

HQL will be described and compared between all treatment arms utilizing the FACT-BMT self report, transplant specific questionnaire and the generic quality of life tool (SF-36). The questionnaires will be scored according to standard procedures. The self report questionnaires will be completed yearly until disease progression. Only English and Spanish speaking patients are eligible to participate in the HQL component of this study.

## CHAPTER 4

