2.8 General Analysis Guidelines

There are no planned sub-group analyses or sensitivity analyses.

Any changes to the planned analyses or any ad hoc analyses will be documented and clarified in each analysis report (through the time of the report) and may be documented in updated versions of the SAP. Ad hoc analyses will be included as supplemental exhibits and noted to be analyses that are not part of the pre-planned analyses.

There are no pre-defined ancillary studies for the BMT CTN 07LT protocol. Optional research samples for future analysis are being collected for those enrolled in 07LT. Any analyses with these samples will be described separately and will be conducted at time points not affecting the analyses described in this SAP.

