The event is the development of the first SPM post randomization on BMT CTN 0702, excluding non-melanoma skin cancers. Death without SPMs will be considered a competing risk for this event. The analysis population is the 0702-enrolled population, and CIBMTR data will be used to supplement BMT CTN 0702/07LT data. Start time is randomization on BMT CTN 0702. Cumulative incidence function will be used to calculate this endpoint and time of randomization on the BMT CTN 0702 protocol will be the starting point for the analysis. Estimates at 5 years will be described along with 98.3% confidence intervals. The cumulative incidence of SPMs will be compared between treatment arms using stratified two-sided Gray's test in pairwise comparisons of treatment groups. SPMs will also be described by histologic type. It will be

noted that reporting of SPM is not required after progression, and the CIBMTR data will be used to supplement 07LT data.

Unexpected Grades 3-5 Adverse Events

Unexpected grades 3-5 adverse events occurring post enrollment on BMT CTN 07LT will be tabulated and compared across treatment arms and lenalidomide status for participants enrolled in BMT CTN 07LT. CIMBTR data will not be used. AEs will be described using the Medical Dictionary for Regulatory Activities (MedDRA) and classified according to the system organ class and preferred term. Summaries by type and severity by treatment arm will be provided, and tabulations will be separated into tables for those who initiated maintenance on BMT CTN 07LT and those who did not.

Health Quality of Life

Health quality of life (HQL) will be compared between all treatment groups utilizing the FACT-BMT self-report, transplant-specific questionnaire and the generic quality of life tool, the SF-36. Only English and Spanish speaking patients are eligible to participate in the HQL component of this trial. Participants were not required to complete the HQL questionnaires after progression; therefore, only HQL completed prior to progression will be summarized. The limitations in interpretation of this analysis will be noted with the presentation of the results. HQL at each time point from BMT 0702 baseline through 5 years post randomization on BMT CTN 0702 will be summarized using simple descriptive statistics (median, mean, SD or SE). No formal statistical analyses will be conducted. As 5 year data is only available for those participants on 07LT, this analysis will focus solely on 07LT participants.

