5. Template of Proposed Table/Figure/Listing (TFL) Shells

The templates for the Tables, Figures, and Listings are provided in the Appendix of this SAP. These templates are for illustration purposes only, and may not be the final layout or wording chosen for publications or presentations. Actual format of the tables and figures may differ and will be subject to change in the final analysis report and/or publication. Editorial changes in presentation or content will not necessarily be described in the changes to planned analyses section of the report or SAP updates.

6. References

Cox D. Regression models and lifetables (with discussion). Journal of the Royal Statistical Society 1972; Series B:187-220.

Gray RJ. A class of K-sample tests for comparing the cumulative incidence of a competing risk. Annals of Statistics 1988, 16: 1141-1154.

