			/Auto	Aut	o/RVD	Auto	/Maint		
		N	%	N	%	N	%	T	otal
All Unexpected Grades 3-5 Adverse Events		XX	100.0	XX	100.0	XX	100.0	XX	100.0
System Organ Class	Preferred								
(SOC)	Term								
SOC1	ALL	XX	XX.X	XX	XX.X	XX	XX.X	XX	XX.X
	PT1		(just N)		(just N)		(just N)		(just N)
	PT2		(just N)		(just N)		(just N)		(just N)
SOC2	ALL	XX	XX.X	XX	XX.X	XX	XX.X	XX	XX.X
	PT1		(just N)		(just N)		(just N)		(just N)
	PT2		(just N)		(just N)		(just N)		(just N)
(etc.)	(etc.)								
Severity									
Grade 3		XX	XX.X	XX	XX.X	XX	XX.X	XX	XX.X
Grade 4		XX	XX.X	XX	XX.X	XX	XX.X	XX	XX.X
Grade 5		XX	XX.X	XX	XX.X	XX	XX.X	XX	XX.X

Exhibit 07LT-10: Health Quality of Life: FACT-BMT for BMT CTN 07LT English/Spanish-Speaking Participants

Note: The analysis is limited to questionnaires for BMT 07LT-enrolled participants who have not died or progressed. The interpretation of results is limited. Questionnaires not completed within the analysis target window are excluded.

							Healin	ent Arn	1				
i			Auto/Aut	o (N=X)	XX)		Auto/RVI	CX=N) C	(X)		Auto/Mai	nt (N=X	XX)
		N	Median	Mean	StdErr	N	Median	Mean	StdErr	N	Median	Mean	StdErr
	Baseline												
Concerns (10 Items)	R1Y												
	R2Y												
	R3Y												
	R4Y												
	R5Y												
FACT-G Total (27	Baseline												
	R1Y												
	R2Y												
	R3Y												
	R4Y												
	R5Y												
FACT-BMT Total (37	Baseline												
	R1Y												
	R2Y												
	R3Y												
	R4Y												
	R5Y												
FACT-BMT Trial	Baseline												
Outcome	R1Y												
Index (24 Items)	R2Y												
	R3Y												
	R4Y												
	R5Y												

Figures may also be provided.

Exhibit 07LT-11: Health Quality of Life: SF-36 for BMT CTN 07LT English/Spanish-Speaking Participants

Note: The analysis is limited to questionnaires for BMT CTN 07LT-enrolled participants who have not died or progressed. The interpretation of results is limited. Questionnaires not completed within the analysis target window are excluded.

							Treatm	ent Arn	n				
			Auto/Aut	o (N=X	XX)		Auto/RVI	D (N=X)	(X)		Auto/Mai	nt (N=X	XX)
		N	Median	Mean	StdErr	N	Median	Mean	StdErr	N	Median	Mean	StdErr
Physical	Baseline												
Well-Being (7 Items)	R1Y												
(1 1001110)	R2Y												
	R3Y												
	R4Y												
	R5Y												
Social / Family	Baseline												
Well-Being	R1Y												
(7 Items)	R2Y												
	R3Y												
	R4Y												
	R5Y												
Emotional Well-Being	Baseline												

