(6 Items)	R1Y												
	R2Y												
	R3Y												
	R4Y												
	R5Y												
Functional Well-Being	Baseline												
(7 Items)	R1Y												
	R2Y												
	R3Y												
	R4Y												
	R5Y												

Figures may also be provided.

Supplemental Exhibit 07LT-1: Enrollment

A table will be provided showing actual yearly accrual for each 07LT participating center from 07LT study initiation to accrual closure.

A table will be provided showing time to last contact summarized separately for participants enrolled on BMT CTN 07LT, and for participants not enrolled on BMT CTN 07LT.

Supplemental Exhibit 07LT-2: Significant Protocol Deviations

A table listing significant protocol deviations/violations will be provided separately for those who continued lenalidomide maintenance therapy on 07LT and those who did not, by treatment group for participants enrolled on 07LT.

Supplemental Exhibit 07LT-3: Permanent Discontinuation of Lenalidomide

A table will be provided to describe the reasons for permanent discontinuation of lenalidomide maintenance therapy for BMT CTN 0702-enrolled participants who initiated therapy on BMT CTN 07LT. For participants who have confirmed they continued on commercial lenalidomide, discontinuation data will be based on discontinuation of commercial lenalidomide.

Supplemental Exhibit 07LT-4: Primary Cause of Death

A table summarizing the primary cause of death by treatment group will be provided; the table will be separated into adjudicated deaths and unadjudicated deaths. Primary cause of death is adjudicated by the BMT CTN 0702 Endpoint Review Committee (ERC) for most participants who died within 38 months of enrollment on 0702. For deaths where cause is not adjudicated by the ERC, if the participant progressed prior to death without a secondary malignancy, cause of death will be reported as progression; if the person progressed prior to death and also reported an SPM, cause of death will be reported as progression/SPM; if the person did not progress prior to death but reported an SPM, cause of death will be reported as SPM; if the person did not progress prior to death and did not report an SPM, site-reported cause of death will be reported.

	Treatment Arm					Total		
	Auto/A	uto	Auto/RVD		Auto/Maint			
	N	%	N	%	N	%	N	%
Enrolled	247	100.0	254	100.0	257	100.0	758	100.0
Total deaths								
Deaths adjudicated by BMT CTN 0702 ERC								
Deaths not adjudicated by BMT CTN 0702 ERC								

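### SAP Exhibit 07LT-11 is titled SF-36, but all its rows are FACT-G subscales, and it shows neither PCS nor MCS, the SF-36 outcome measures set by Protocol 3.3.5 (low severity)

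*SAP*

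**What the plan says.** Protocol 3.3.5 uses two quality-of-life instruments and fixes the outcome score for each.

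- FACT-BMT: the FACT-BMT Total "will be used as the outcome measure in summarizing the FACT-BMT data". Of the core questionnaire inside it, the protocol says: "The FACT-G consists of four subscales developed and normed in cancer patients: Physical Well-being, Social/Family Well-being, Emotional Well-being, and Functional Well-being".
- SF-36: after listing eight components, the protocol states that "the Physical Component Summary (PCS) and Mental Component Summary (MCS) will be used as the outcome measures in summarizing the SF-36 data". The reason given is comparison with published norms.

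SAP 4.2 (Health Quality of Life) says the arms will be compared using the FACT-BMT and the SF-36. It names no score for either. It limits the summary to 07LT participants before progression, from 0702 baseline to 5 years, and adds: "No formal statistical analyses will be conducted".

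The scores appear only in the SAP Appendix. Exhibit 07LT-10 (FACT-BMT) has rows for BMT Concerns, FACT-G Total, FACT-BMT Total and the Trial Outcome Index. The next shell is headed "Exhibit 07LT-11: Health Quality of Life: SF-36 for BMT CTN 07LT English/Spanish-Speaking Participants". Its row groups are the Physical, Social/Family, Emotional and Functional Well-Being scales, each at Baseline and R1Y to R5Y.

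SAP Section 5 says of all the shells: "These templates are for illustration purposes only, and may not be the final layout or wording chosen for publications or presentations".

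**The concern.** The title of Exhibit 07LT-11 and its rows belong to different instruments. Because SAP 4.2 names no scores, the shells are the only place in the SAP where a programmer can see which quality-of-life scores are to be tabulated. For the FACT-BMT that works, since Exhibit 07LT-10 carries the protocol's outcome score. For the SF-36 it does not, since the one table meant for it shows scores from the other questionnaire.

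If the shell were populated as drawn, readers of the report would see FACT-G subscale scores labelled as SF-36 results, and neither PCS nor MCS would be reported. Quality of life is a stated secondary objective and the SF-36 is one of its two instruments. What is at stake is the accuracy of a descriptive secondary table.

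**Working it through.** No sample-size, power or error-rate figure bears on this point. The check is a comparison of labels and item counts.

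**1. Item counts.** Inputs from Exhibit 07LT-11: Physical 7, Social/Family 7, Emotional 6, Functional 7. Inputs from Exhibit 07LT-10: BMT Concerns 10, FACT-G Total 27, FACT-BMT Total 37, Trial Outcome Index 24.

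- Sum of the four row groups: 7 + 7 + 6 + 7 = 27, equal to the FACT-G Total.
- Adding BMT Concerns: 27 + 10 = 37, equal to the FACT-BMT Total.
- Physical + Functional + BMT Concerns: 7 + 7 + 10 = 24, equal to the Trial Outcome Index.

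The rows under the SF-36 title therefore reproduce the printed FACT-G and FACT-BMT totals exactly.

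**2. Labels.**

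| Row group in Exhibit 07LT-11 | FACT-G subscale in Protocol 3.3.5? | SF-36 component or summary in Protocol 3.3.5? |
|---|---|---|
| Physical Well-Being | Yes | No |
| Social / Family Well-Being | Yes | No |
| Emotional Well-Being | Yes | No |
| Functional Well-Being | Yes | No |

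The eight SF-36 components in the protocol have other names, such as Role Physical and Vitality. Result: 4 of 4 row groups are FACT-G, 0 of 8 SF-36 components appear, and 0 of 2 SF-36 outcome measures (PCS, MCS) appear.

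**3. Whether other SAP text fills the gap.** SAP 4.2 names the SF-36 as an instrument and gives the descriptive statistics, but no score. PCS, MCS and the term component summary occur nowhere in the SAP. SAP 2.8.1, which lists changes and clarifications relative to the protocol, does not mention the quality-of-life measures.

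**4. Whether rows were lost from the table.** The last row group, "Functional Well-Being", runs to R5Y and is followed by the same closing remark about figures as Exhibit 07LT-10. The contents list puts Exhibits 07LT-10 and 07LT-11 on pages 30 and 31, and the first supplemental exhibit on page 32. The shell reads as complete.

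**The case against.** The strongest reply is that this is one mislabelled illustrative shell. Much of that stands.

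- SAP 4.2 requires the SF-36 to be used, so printing FACT-G scores in its place would breach SAP 4.2. The predicted error rests on the shell alone, and SAP Section 5 says the final tables may differ from the shells.
- Protocol 3.3.5 still defines PCS and MCS, and nothing in the SAP revokes it. The protocol's own analysis section (5.4) also leaves the scores unnamed, and the SAP 4.2 sentence on the instruments follows it closely. SAP 4.2 does not name FACT-BMT Total either.
- Quality of life is descriptive, restricted to 07LT participants before progression, and to be presented with its limitations noted.

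A reader might infer that the SAP has dropped PCS and MCS or replaced them with FACT-G subscales. The documents do not support that. SAP 2.8 promises that "Any changes to the planned analyses or any ad hoc analyses will be documented and clarified in each analysis report", and SAP 2.8.1 lists no change to these measures. Its silence fits the protocol measures remaining in force.

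What the reply does not remove is the mismatch itself. The note that shells are illustrative allows the layout or wording to change, but it does not say which scores belong in the SF-36 table. The only SAP content that does so points to the wrong instrument.

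**Conclusion.** The point holds as a protocol-SAP inconsistency of low severity. Exhibit 07LT-11 is wrong as written: all 4 row groups belong to the FACT-G, and 0 of the 2 SF-36 outcome measures set by the protocol are shown.

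The reporting error follows only if the shell is populated as drawn. An analyst who works from Protocol 3.3.5 would avoid it. No hypothesis test, error rate or primary conclusion is affected, because the comparison is descriptive and secondary. The conclusion assumes that the shell is complete as printed, which its last row, its closing line and the contents-list pages support.

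**What to change.** 1. Replace the rows of Exhibit 07LT-11 with SF-36 PCS and SF-36 MCS at Baseline and R1Y to R5Y, keeping the existing columns.
2. If the four FACT-G subscales are wanted, move them to Exhibit 07LT-10, where the FACT-BMT Total already is.
3. In SAP 4.2, name FACT-BMT Total, PCS and MCS as the quality-of-life outcome measures, or cross-refer to Protocol 3.3.5.

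No entry in SAP 2.8.1 is needed, because the correction restores the protocol's measures and is not a departure from them. The cost is one table shell and a sentence of SAP text. The SF-36 is already in the protocol's assessment plan, so no visit, form or instrument is added.

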#### 4.3.3. Reporting Patient Deaths

Recipient Death Information must be entered into AdvantageEDC within 24 hours of knowledge of the patient's death for patients who are enrolled in the long-term follow-up protocol. If the cause of death is unknown at that time, it need not be recorded at that time. However, once the cause of death is determined, the form must be updated in the web-based data entry system. Patients who do not consent or who have progressed on the BMT CTN 0702 protocol will have deaths reported through the standard CIBMTR reporting mechanism.

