ERC-Adjudicated Deaths								

		Tre	eatmen	t Arm			Т	otal
	Auto/	Auto	Auto	o/RVD	Auto	o/Maint		
	N	%	N	%	N	%	N	%
Primary Cause of Death								
Disease Recurrence or Persistence								
Secondary Malignancy								
[Reason 3]								
[Reason 4]								
Deaths with Cause Not Adjudicated								
Primary Cause of Death								
Disease Recurrence or Persistence								
Secondary Malignancy								
Disease recurrence or persistence/secondary malignancy								
[Reason 4]								
[Reason 5]								

Supplemental Exhibit 07LT-5A: Multivariate Cox Regression Analysis of Overall Survival – 0702 baseline factors

Maximum Likelihood Estimates and Hazard Ratios

		Hazard Rati	0	
Covariate	Point	Confidence	Confidence	Model
	Estimate	limit	limit	Parameter
				Estimate
				p-value
Auto/Auto treatment arm vs				
Auto/Maintenance arm ¹				
Auto/Auto treatment arm vs				
Auto/RVD arm ¹				
Auto/RVD treatment arm vs				
Auto/Maintenance arm ¹				
Risk strata—High risk vs				
Risk strata—Standard risk				
(other adjustment factor as				
needed)				
(other adjustment factor as				
needed)				
(other adjustment factor as				
needed)				

¹P-values are compared to the 0.05/3 significance level.

Figure: A forest plot for the hazard ratios and confidence intervals may also be provided.

Notes for this secondary analysis:

Model covariates:

- Treatment group
- Randomized risk strata
- Any of the factors in column 2 of the table in Section 3.1 that have a test for treatment group differences that is significant at the 0.1 level. ERC-adjudicated baseline disease response will be tested using 2 categorizations (CR or better, VGPR or better). If both are significant at the 0.1 level, the one that is more significant will be used in the model.
- No interactions will be included.

- Analysis population is 0702 participants
- Time to OS is calculated from randomization
- proc phreg in SAS, no model selection procedures

Supplemental Exhibit 07LT-5B: Multivariate Cox Regression Analysis of Overall Survival from Initiation of Lenalidomide

Maximum Likelihood Estimates and Hazard Ratios

		0		
Covariate	Point Estimate	Lower Confidence Limit	Upper Confidence Limit	Model Parameter Estimate p-value
Auto/Auto treatment arm vs Auto/Maintenance arm ¹				
Auto/Auto treatment arm vs Auto/RVD arm ¹				
Auto/RVD treatment arm vs Auto/Maintenance arm ¹				
Risk strata—High risk vs Risk strata—Standard risk				
Permanent discontinuation of lenalidomide (time-dependent)				

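### For deaths the review committee did not adjudicate, the cause-of-death table reports event history as cause, so it can mislabel deaths as due to SPM or progression

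*SAP*

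**What the plan says.** The exhibit tabulates primary cause of death by randomized arm for all 758 patients randomized on 0702. The Endpoint Review Committee (ERC) adjudicates cause "for most participants who died within 38 months of enrollment on 0702". Every other death follows four branches:

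- Progression, no SPM: "if the participant progressed prior to death without a secondary malignancy, cause of death will be reported as progression".
- Progression and SPM: "if the person progressed prior to death and also reported an SPM, cause of death will be reported as progression/SPM".
- SPM, no progression: "if the person did not progress prior to death but reported an SPM, cause of death will be reported as SPM".
- Neither: "if the person did not progress prior to death and did not report an SPM, site-reported cause of death will be reported".

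The SAP also states that "the table will be separated into adjudicated deaths and unadjudicated deaths". In the shell, both blocks are headed as primary cause of death and both carry the consecutive rows "Disease Recurrence or Persistence Secondary Malignancy". The unadjudicated block adds a row for the combined category.

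Protocol 4.3.3 has sites enter death information for patients enrolled on the long-term follow-up protocol, and "once the cause of death is determined, the form must be updated in the web-based data entry system". Deaths in patients who did not consent, or who progressed on 0702, are reported through CIBMTR. SAP 2.2 says data from 0702, 07LT and CIBMTR all feed the cause-of-death table. SAP 2.8 plans no sensitivity analyses.

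**The concern.** A primary cause of death should say what the patient died of. Three of the four branches say only what had happened to the patient earlier. A progression-free patient whose SPM was treated and who then dies of a cardiac event must appear under secondary malignancy, whatever the site recorded. Likewise, a patient who met a progression criterion and later dies of something unrelated appears under progression.

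This matters most in the period that 07LT adds. Follow-up-only entry is at 4 years post-randomization (Protocol 2.3.1), and maintenance entry needs 3 completed years of maintenance (Protocol 2.3.2). Few deaths on 07LT would therefore fall inside the 38-month adjudication window.

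The same row label also means two things. In the adjudicated block it is a committee judgement. In the other block it means that an SPM was reported and progression was not. The shell has no footnote saying so. The protocol puts emphasis on SPMs (1.4), and this exhibit is where deaths are attributed to them, so a reader could take the row at face value.

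**Working it through.** No sample size, power or alpha in the plan depends on this rule, so there is no stated figure to reproduce. The check has two parts.

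**1. Trace the branches for an unadjudicated death.**

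| Progression | SPM reported | Row assigned | Site cause used? |
|---|---|---|---|
| Yes | No | Progression | No |
| Yes | Yes | Progression/SPM | No |
| No | Yes | SPM | No |
| No | No | Site-reported cause | Yes |

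No branch asks when the event occurred, whether the SPM was active at death, or whether it led to the death. The fourth branch shows that the SAP treats the site-reported cause as available and usable.

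**2. Illustrate the possible miscount.** The death counts in the shell are blank, so every value here is an assumption.

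- A = unadjudicated deaths with an SPM and no progression; qA = share of A actually due to the SPM.
- B = unadjudicated deaths with both events; qB = share of B actually due to the SPM.
- SPM deaths among patients with a reported SPM = A·qA + B·qB.
- The rule puts A in the SPM row and B in the combined row.

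*Progression-free branch alone.* Overcount = A(1 − qA), a relative excess of 1/qA − 1. This is never negative: 0% at qA = 1.0, 11% at 0.9, 43% at 0.7, 100% at 0.5.

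*SPM row as a whole.* Row minus SPM deaths = A − (A·qA + B·qB) = A(1 − qA) − B·qB.

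| A | B | qA | qB | A(1 − qA) | B·qB | Net error |
|---|---|---|---|---|---|---|
| 10 | 5 | 0.5 | 0.2 | 5.0 | 1.0 | +4.0 |
| 10 | 5 | 0.7 | 0.5 | 3.0 | 2.5 | +0.5 |
| 10 | 5 | 0.9 | 0.8 | 1.0 | 4.0 | −3.0 |
| 10 | 10 | 0.5 | 0.2 | 5.0 | 2.0 | +3.0 |
| 10 | 10 | 0.7 | 0.5 | 3.0 | 5.0 | −2.0 |
| 10 | 10 | 0.9 | 0.8 | 1.0 | 8.0 | −7.0 |

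The sign depends on the mix.

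*SPM and combined rows added.* The total A + B cannot be below A·qA + B·qB. With A = 10, B = 5, qA = 0.7 and qB = 0.5 it is 15 against 7 + 2.5 = 9.5.

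**A related conflict.** SAP 4.2 and the footnote to Exhibit 07LT-8 say SPM reporting is not required after progression. Protocol 4.3.1.1 says it continues to the end of follow-up. If a post-progression SPM is not captured, a death from it falls in the progression row, which lowers the SPM row further. The two passages need reconciling.

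**Progression branch.** Protocol 3.1 allows progression on paraprotein level alone. Protocol 1.2 cites median survival after first progression of 29 and 48 months in the two arms of an earlier maintenance trial. There can thus be years in which a death from another cause would be labelled progression.

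**The case against.** A reader might infer that the rule overstates SPM deaths in the table generally. The documents do not support that. Deaths with both events have their own row, so genuine SPM deaths after progression leave the SPM row, and the net error can be negative.

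A reader might also think that early and late deaths are pooled under different rules. They are not: the two sources sit in separate blocks, and the rule is disclosed.

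Nor does this threaten a main safety result. SPM mortality is not an endpoint in either document. The SPM endpoint is cumulative incidence of first SPM. The table is untested and arranged by randomized arm, and all arms were to receive maintenance, so it cannot isolate deaths due to long-term lenalidomide. The rule is the same in every arm, and no between-arm bias is claimed here.

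A fixed rule is also a defensible choice when sites attribute causes unevenly. An infection death during SPM treatment may be recorded as infection although the SPM was the underlying cause, so disagreement with the site is not proof of error. Non-melanoma skin cancers need not be reported, which removes one obvious group of non-fatal SPMs. The duty to update the cause in Protocol 4.3.3 covers only 07LT enrollees. What CIBMTR holds for the others cannot be seen from these documents.

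All of this stands and limits the point to labelling and transparency. It does not answer the mismatch between a heading that promises cause of death and rows that report event history, with the recorded cause set aside and no alternative view planned.

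**Conclusion.** The point holds as a minor one. For unadjudicated deaths with prior progression or a reported SPM, the SAP replaces the recorded cause with event history and sets no timing or causal condition. Among progression-free patients the SPM count can only equal or exceed the deaths actually due to SPM. Deaths from other causes can be labelled progression. For the SPM row as a whole the direction is not determined.

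The size cannot be estimated from the documents. The figures above illustrate direction and rest wholly on assumed values of A, B, qA and qB. PFS, OS, EFS and SPM incidence are unaffected.

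**What to change.** In Supplemental Exhibit 07LT-4, for non-adjudicated deaths:

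- Show the site-reported (or CIBMTR-reported) cause beside the derived category, with a row for missing or unknown. Neither column need be declared the main one.
- Relabel the derived rows as event history, for example 'death with prior SPM', 'death after progression' and 'death after progression and SPM'.
- Add a footnote stating the rule and that the adjudicated block rests on committee judgement.

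SAP section 5 already treats the shells as illustrative, so the layout can change easily; the classification text above the table should be revised with it.

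The cost is one extra column. The downside is that site-reported causes vary in quality and may be missing for some patients followed only through CIBMTR. Setting the two columns side by side makes that visible.
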